Layered stigma is associated with worse outcomes than HIV stigma alone. Stigma is best understood as a dynamic social process rather than an individual attribute.^{27,28} When stigma is layered, social devaluation from two socially discrediting conditions can operate synergistically. Households undergoing TB contact investigation face or anticipate facing at least two stigmatized conditions, HIV and TB. TB-HIV stigma has consequences for TB care-seeking, TB-HIV outcomes, and HIV management.²⁹

Uganda provides a representative setting for expanding and improving home HIV testing by reducing household stigma for HIV & TB. Uganda is a high HIV-TB-burden country, with estimated HIV prevalence of 7.1% and TB prevalence of 253 per 100,000. More than 25% of PLWH are unaware of their HIV status.³⁰ Uptake of door-to-door home HIV testing ranges from 69%–95%^{7,8,13}, but uptake of HIV testing among household contacts of TB patients is only 53%.²⁰ The PLWH Stigma Index found that >60% of Ugandan PLWH experienced malicious gossip in their family or community in the past year and nearly 10% had been excluded from family activities.³¹ TB stigma may be even more common in Uganda; nearly 50% of survey respondents hold stigmatizing attitudes toward TB, compared to 26% with stigmatizing attitudes toward HIV.³²

There is a need to build awareness of and capacity for integrating stigma hypotheses and measures into research on HIV-TB in Uganda. We propose two specific capacity-building initiatives that will draw on experiences building capacity for mixed-methods and implementation research through our Fogarty D43 Pulmonary Complications of AIDS Research Training program. First, we will sponsor a doctoral student from Makerere University to work on this project. Second, each year, we will sponsor a symposium highlighting current research and future priorities in HIV and TB stigma at the Makerere Joint Annual Science and Health Conference at Makerere University, and include patients, families, researchers, and program officials.

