LHWs will carry out home visits in pairs or with 3 LHWs dependent on the needs of that household. A LHW employed by the clinics will provide routine contact investigation services and a trained study LHW will collect research data and deliver the intervention for those randomized to the intervention arm of the study. While the LHW carries out standard contact investigation screening, the study LHW will administer a short HIV-TB stigma scale individually to all consenting adult members of the household in both arms. The research LHW will follow the assigned script based on randomization allocation to identify household members who are eligible and invite them to test for HIV, recording time-stamped offers, test decisions, and test results. The research LHW will collect household- and individual-level demographic, socioeconomic data, stigma scales, measures of household stability, including household tenure in years as well as relationship to and perceived influence of household members and clinical data using a structured survey.

Procedures for all households: Upon arrival, the CHWs will enroll all eligible, consenting household contacts in the study. But before doing this, at the start, CHWs will introduce themselves and ask for introduction of contacts. At this time the master list of all the contacts will be created.

- They will introduce the reason for their visit and the services they will offer (TBCI, oral HIV testing) using the introductory script for either Intervention or Routine Contact Investigation households, depending on the household assignment.
- For the intervention arm, one CHW will take the index case to a private area to ask the influence questions using the paper form (master list) as a key. After completing this exercise, the CHW will then embark conducting household contact screening interviews followed by HIV testing and any other study related activities. All data will be collected via CommCare.
- Meanwhile, the other CHW will be conducting routine TB contact investigation activities and any other clinical procedures in household TB contact investigation. Details of these procedures are found below:

a) Index case influence questions

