After enrollment, CHWs will introduce themselves and ask for the introduction of contacts and it is at this time when a contacts master list will be created. Index patients will then be asked the influence questions. The questions will be asked in two steps, once to capture the number and once to capture the name. The other CHW will go head to conduct routine TB contact investigation activities.

b) Household contact screening interview

After household contact enrolment, each contact will undergo a short interview. This interview will capture age, gender, occupation (if applicable), income (if applicable), education in years, relationship to index patient, history of testing for HIV, month and year of last HIV test, and self-reported symptoms of TB (including cough, subjective fever, or weight loss).

The short (13-item) version of the Van Rie TB- and HIV-related stigma scales will be administered immediately prior to TB screening, as well as at the conclusion of the visit. We will ask the index patient to share the number of rooms in the dwelling, the number of windows in the dwelling, and the number of individuals (including children) who dwell there. All screening interview components will be conducted by a CHW. Screening interview components are identical for all study groups.

c) HIV testing procedures

Working in teams of two, CHWs will provide household contact investigation services, including offering oral HIV testing. One CHW will lead and accompany each HIV test while a colleague leads other household members through TB screening.

To begin, the CHW responsible for offering HIV testing will individually invite the client to a place apart from the others. S/he will detail the process of HIV testing in Luganda and/or English, per client preference. A pictorial guide may be used to help walk the client through each step of the process using a Luganda- or English-language guide. The CHW will then provide pre-test counselling.

Consenting household contacts who choose to test for HIV will swab their own gums. CHWs will be fully trained to provide HIV counselling and support throughout all testing procedures.

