1. The test statistic is the effect regression coefficient from a mixed-effects logistic regression model
2. Alpha = 0.05
3. Power = 90%
4. The proportion consenting to testing in the control group will be 0.85
5. The proportion consenting to testing in the intervention group will be 0.98 (a difference of +0.13 vs the control group).
6. An average of two household contacts will be eligible for HIV testing per household. The intra-class correlation (ICC) will be 0.59.

The total number of households needed is sensitive to the mean cluster size. Under the preceding assumptions, the necessary number of households may range from 152 if the mean number of eligible contacts per households is 2 to 138 if the mean number of contacts per household is 3. The total

number of households needed is also sensitive to the ICC. Sample size estimates assuming a range of possible ICC values, ranging from the value observed during the preliminary research (0.59) to higher values (0.65, 0.70), are not presented here although considered by the study team. Finally, the total number of households needed is sensitive to the baseline (control group) proportion of tests accepted. Sample size estimates assuming three possible baseline testing rates (75%, 80%, and 85%) in control group households have been considered. We will plan an interim blinded power analysis by an external biostatistician to readjust sample size targets as necessary for actual mean cluster size and ICC after enrolling the first 100 households.

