All patients and their household contacts will receive a verbal invitation to participate in accordance with National TB guidelines. Additionally, all willing and eligible index patients and their household contacts will be asked to review the research study information sheet /verbal informed consent document outlining all study related activities, then provide verbal consent to participate in the study. Lay health workers trained in administering informed consent procedures, Human Subjects' Protection and Good Clinical Practice will carry out and document all verbal informed consent encounters. For participants under age 18 who do not meet the definition of an emancipated minor, permission to participate will be obtained from a parent or legal guardian. Among index patients, children aged 14-17 must provide assent to participate after their parent provides permission. Among contacts, only household members 15 years of age or older will be eligible for HIV testing; those aged 15-17 must provide assent to participate after their parent provides permission.

After a participant agrees to participate and/or a parent provides permission, the lay health worker will carry out the routine contact investigation procedures, recording clinical and demographic information about the patient on an electronic tablet. This information will include names and ages of all household members, contact telephone numbers for the index patient and a treatment supporter.

7. **Evaluation of Subject(s) Capacity to Provide Informed Consent/Accent:** Indicate how the personnel obtaining consent will assess the potential subject's ability and capacity to consent to the research being proposed.

8. **Non-English Speaking Subjects:** Explain provisions in place to ensure comprehension for research involving non-English speaking subjects. If enrollment of these subjects is anticipated, translated copies of all consent materials must be submitted for approval prior to use.

Subjects who do not speak English or Luganda will be excluded from this formative study. All LHWs administering study protocol will be fluent in both English and Luganda. All consent forms will be available in both English and Luganda and will be administered in the language of preference.

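### Prior HIV diagnosis is not a listed data item in Aim 2, so new and known positives cannot be reliably separated, and the planned 98% uptake depends on an undefined denominator

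*Combined protocol and SAP*

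**What the plan says.** Section I.4 (Household-Randomized controlled trial) has the research worker follow the assigned script to "identify household members who are eligible and invite them to test for HIV". Section III.6 gives the one explicit condition for the test: "only household members 15 years of age or older will be eligible for HIV testing". The Aim 2 contact criteria in Section I.8 are likewise household contact status and age 15 or older, with no exclusion at contact level.

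The contact screening interview in Section I.4 lists "history of testing for HIV, month and year of last HIV test" among its items. Section IV, item 1, gives much the same list. Neither names the last result, known HIV status or current HIV care. The paragraphs on HIV test results and referral in Section I.4 have no branch for someone already diagnosed.

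Aim 2 in Section I.1 nevertheless promises the yield of HIV diagnoses and the proportion of new PLWH linked to care at 1 month.

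The sample size in Section I.4 rests on uptake: "The proportion consenting to testing in the control group will be 0.85", "The proportion consenting to testing in the intervention group will be 0.98", "An average of two household contacts will be eligible for HIV testing per household" and "The intra-class correlation (ICC) will be 0.59". These values are attributed to Aim 1 data. The denominator used there is not described.

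**The concern.** A contact who already knows that he or she is HIV-positive can affect the results in one of two ways. One who declines the offer lowers measured uptake for a reason that the intervention is not designed to change. One who accepts adds a positive result that is not a new diagnosis and, if already in care, may be counted as linked. The same person cannot do both, but either behaviour distorts an outcome.

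If prior diagnosis is not recorded at the visit, it cannot be reconstructed reliably at analysis. At stake are the meaning of the yield and linkage figures and the power of the uptake comparison, which is the comparison that sets the sample size.

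**Working it through.** **Inputs from the plan.** Uptake 0.85 and 0.98, ICC 0.59, mean cluster size m = 2, alpha 0.05, power 90%, 152 households and 304 contacts (Section I.4, Sample Size). National HIV prevalence 7.1%, and "More than 25% of PLWH are unaware of their HIV status" (Section I.3).

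**Assumptions.** The test is two-sided (the plan does not say). The national figures apply to these contacts. The share of known positives who decline is not given, so it is varied.

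**Reproducing the plan.** Contacts per arm before clustering, with p̄ the mean of the two rates:

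n = [1.96√(2p̄(1−p̄)) + 1.2816√(p1(1−p1) + p2(1−p2))]² / (p1−p2)²

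- With 0.85 and 0.98, n = 94.6.
- The design effect is 1 + (m−1)×0.59. At m = 2, 94.6 × 1.59 / 2 = 75.2, so 76 households per arm, or 152 in total. This matches the plan.
- At m = 3, 94.6 × 2.18 / 3 = 68.8, so 69 per arm, or 138. This also matches.
- At 152 households the effective number per arm is 152 / 1.59 = 95.6. Power is Φ{[|p1−p2|√95.6 − 1.96√(2p̄(1−p̄))] / √(p1(1−p1) + p2(1−p2))} = Φ{(1.271 − 0.773) / 0.3835} = 0.903.

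**Known-positive share.** At most 75% of people living with HIV are aware, so k = 0.071 × 0.75 = 0.053, the upper value on these figures.

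**Yield.**
- Expected positives: 304 × 0.071 = 21.6.
- Already known: up to 304 × 0.053 = 16.2.
- New: about 5.4.
- If everyone tested, up to 75% of the positives would be prior diagnoses.

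**Uptake.** If a fraction d of known positives decline and stay in the denominator, uptake cannot exceed 1 − kd. So 0.98 is unattainable once kd > 0.02, which at k = 0.053 means d above 0.02 / 0.053 = 38%. Taking 0.85 and 0.98 as the rates among contacts not known to be positive, each overall rate is p(1−k) + k(1−d):

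- **All decline (d = 1).** The ceiling is 94.7% and the rates are 0.805 and 0.928. Power = Φ{(1.203 − 0.943) / 0.473} = 0.71. For 90% power, n = 158.6 and 158.6 × 1.59 / 2 = 126.1, so 254 households.
- **Half decline (d = 0.5).** The ceiling is 97.3% and the rates are 0.831 and 0.954. Power is 0.79. For 90% power, n = 130.6 and 130.6 × 1.59 / 2 = 103.8, so 208 households.
- **Smaller share, k = 3% (assumed), all decline.** Rates are 0.825 and 0.951, and power is 0.79.
- **Known positives outside the denominator.** The rates stay at 0.85 and 0.98, and m falls to 2 × 0.947 = 1.89. Power at 152 households is about 0.90, and about 154 households are needed.

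**If the Aim 1 rate of 0.85 already included known positives.** Dilution of the control rate does not apply, but the ceiling does. With 0.85 against 0.947, power at 152 households is about 0.60.

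**The case against.** A reader might infer that known-positive contacts definitely remain in the denominator, that their status is never recorded, and that 98% is therefore out of reach. The documents do not support that.

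- **Denominator.** The age rule is a stated condition, not necessarily the whole rule. Section I.9 bases eligibility on routine screening questions whose content is not given, and these could remove known positives. No text says that such contacts are offered a test or scored as not tested.
- **Data capture.** The plan also collects unspecified clinical data, gives those who opt out a survey of unstated content, and has a clinic team recording follow-up in both arms. Status might surface in any of these. The survey is a weak substitute: it comes after the offer, reaches only decliners, and is described under the intervention arm.
- **Size.** The 5.3% comes from national data, not TB households, and the 0.71 needs every known positive to decline. If half rather than three quarters of people living with HIV are aware (an assumption), the share is 0.071 × 0.5 = 3.6%, and power is 0.77 with all declining. The plan says that control rates of 75% and 80% were also considered.
- **Importance.** Section I.4 (Analysis) makes uptake secondary to stigma change, and linkage is descriptive in a pilot. Randomization should balance known positives on average, so keeping them dilutes the contrast rather than biasing it.
- **Remedy.** Making self-reported status define the main denominator would be an exclusion after randomization, based on answers taken by unblinded teams that each serve one arm. It could differ by arm and would conflict with the intention-to-treat analysis in Section I.13.

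All of this stands and limits how the point is worded and fixed. It does not supply a listed item or rule that separates new from prior diagnoses.

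**Conclusion.** The point holds as a gap in data capture and definition. With the items listed, newly diagnosed contacts and their linkage cannot be reliably separated from prior diagnoses. Up to about 16 of about 22 expected positives could be known already, if the national figures carry over.

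The effect on uptake is conditional. The planned 0.98 is unreachable only if known-positive decliners exceed 2% of the denominator. Power of about 0.71 (all decline) or 0.79 (half decline) further assumes a 5.3% known-positive share and that 0.85 and 0.98 describe contacts not known to be positive. It would be wrong to conclude that the trial is underpowered as it stands: neither the known-positive share in these households, nor their refusal rate, nor the Aim 1 denominator is given. If known positives are already outside the denominator, power stays at about 0.90.

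The change is worth making before enrolment, because it affects what the trial can report and cannot be made good afterwards.

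**What to change.** 1. Add one private, optional CommCare item on a prior positive result or current HIV care. Ask it in identical words in both arms before the test offer and, if consent procedures allow, before the arm-specific introductory script. The test offer itself need not change.
2. Define yield and new PLWH as positives with no prior positive result.
3. Keep uptake among all eligible contacts as the intention-to-treat analysis. Add a prespecified analysis restricted to contacts not known to be HIV-positive, and report known-positive counts by arm so that differential disclosure is visible.
4. State which denominator produced the Aim 1 rate of 0.85. If it included known positives, restate the 0.98 and the power.

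The cost is one question, two definitions and one extra analysis. The drawbacks are that the item is sensitive in a study whose named primary risks include disclosure of HIV status, that self-report may be incomplete, and that disclosure could differ by arm. The last is why the restricted analysis should support the intention-to-treat result and not replace it.

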CHW Training We will carry out a participatory training with the study CHWs. First, CHWs will meet as a group to discuss study aims, the trial design, and the importance of study controls. Next, CHWs will be split into Clinic Based CHWs, Intervention CHWs and CHWs doing Routine Contact Investigation. Each group will separately review and role play their assigned procedures. Clinic Based CHWs will be trained to provide TB education and counselling, index patient enrolment, and randomization procedures. Intervention CHWs will be trained to deliver the social-behavioural intervention finalized in Aim 1. Standard of Care CHWs will be trained to deliver a standard offer of opt-in HIV testing. Both Standard of Care CHWs and Intervention CHWs will be trained in the use and delivery of oral HIV testing kits including the delivery of HIV education and counselling.

Household-Randomized controlled trial. LHWs attached to 2 TB units in Kampala Uganda will identify, invite, consent, and enroll approximately 152 consecutive, eligible index patients for household contact investigation for TB. We anticipate these households containing approximately 304 household contacts with approximately 1:1 randomization (half in each study arm). Upon index patient consent, we will collect demographic information from each index patient at enrollment, including age, gender, occupation (if applicable), income (if applicable), education in years, and household composition,

including number, age, gender, relationship to, and perceived influence of self-reported household contacts. After study enrolment and collection of index patient demographic data, a CHW will work with the index patient and, if available, treatment supporter to schedule the home visit. Households will be randomly assigned to one of the two CHW teams to receive the intervention or standard of care. The study CHW will note the self-reported number of household contacts aged 15 or older and requisition the appropriate number of HIV test kits based on the number of reported contacts, adding two extra kits for extra margin.

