In the Aim 2 analysis, we will calculate and compare uptake across each of the trial arms using an intention-to-treat analysis. We will also consider a per protocol analysis and model adjusted for imbalances in baseline confounders as secondary analyses. To test the hypothesis that a norming intervention can increase test uptake, we will compare testing uptake among the intervention households and control households using cluster-adjusted chi-squared tests of proportion and by fitting mixed effects logistic regression models with two levels (household, contact.) To test the hypothesis that invitation scripts that apply acceptance-optimized sequencing of oral test offers and prosocial messaging can decrease HIV stigma within households, we will evaluate change in HIV-TB stigma using cluster-adjusted dependent t-tests and fitting multilevel models with clustered standard errors. We will conduct a causal mediation analysis to determine to what degree the effects of the intervention on stigma explain the improvement in test uptake using observed-variable structural equation modeling. All hypothesis tests will be carried out at alpha of 0.05, corrected for multiple tests as appropriate. We will report household ICC for stigma as well as test uptake and will consider a household ICC of >0.2 a sufficient level of clustering necessitating adjustment.

SECTION II: RESEARCH INVOLVING DRUGS, BIOLOGICS, RADIOTRACERS, PLACEBOS AND DEVICES

If this section (or one of its parts, A or B) is not applicable, check off N/A and delete the rest of the section.

A. RADIOTRACERS N/A

B. DRUGS/BIOLOGICS N/A

B. DEVICES N/A

SECTION III: RECRUITMENT/CONSENT AND ASSENT PROCEDURES**1. Targeted Enrollment: Give the number of subjects:**

- a. Targeted for enrollment at Yale for this protocol: 0
- b. If this is a multi-site study, give the total number of subjects targeted across all sites:
 - 40 to 60 individuals drawn from 20 households (Aim 1)
 - Approximately 8 to 15 lay health workers with experience carrying out TB contact investigation
 - Approximately 60-100 health workers participating in HIV and TB care services during the COVID-19 pandemic
 - Approximately 152 index patients and their approximately 304 household contacts (Aim 2)

2. Indicate recruitment methods below. Attach copies of any recruitment materials that will be used.

 Flyers	 Internet/web postings	 Radio

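### Contacts consent after household allocation, to teams tied to one arm, and the uptake denominator is undefined, so study consent could select contacts differently by arm

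*Combined protocol and SAP*

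**What the plan says.** All references are to the combined protocol and SAP, Section I unless stated.

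- **Allocation.** Item 4, Randomization: after the index patient (or guardian) consents, the community health worker phones the coordinator, learns the arm and contacts that arm's team. Each team always works in the same arm.
- **Recruitment of contacts.** Section III, item 3: contacts are invited during the contact investigation. Item 4, Procedures for all households: "Upon arrival, the CHWs will enroll all eligible, consenting household contacts in the study". The same text puts introductions and a master list of contacts before this step. The visit and the oral HIV test are presented "using the introductory script for either Intervention or Routine Contact Investigation households, depending on the household assignment".
- **A different order.** Item 4, subsection a) on influence questions, puts the introductions and master list after enrolment, without saying whose enrolment.
- **Analysis.** Item 13: the team will "calculate and compare uptake across each of the trial arms using an intention-to-treat analysis". It does not say whether the contacts counted are those listed, eligible, offered a test or enrolled.
- **Sample size.** Item 4, Sample Size, counts eligible contacts: "An average of two household contacts will be eligible for HIV testing per household". There is no allowance for non-enrolment.
- **Roster.** Item 4, Household-Randomized controlled trial: household composition is taken from the index patient at enrolment, "including number, age, gender, relationship to, and perceived influence of self-reported household contacts". Neither this roster nor the master list is tied to the analysis.

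**The concern.** Randomising households protects the comparison only if the contacts analysed do not depend on what happens after allocation. Here a contact learns from an arm-specific team that HIV testing will be offered, and then decides whether to join. Someone who does not want to test can decline the study and keep routine services (Section VI, item 1). The Aim 2 visit procedures say nothing about eligible contacts who are absent; telephone contact is described only for the 3-month follow-up.

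If uptake is then computed among enrolled contacts, a script that turns reluctant people away from the study looks like a script that raises testing. If instead the control approach loses the reluctant, a real benefit is hidden. Uptake is labelled secondary (item 4, Analysis), but the sample size rests on it. The primary stigma outcome passes through the same step, since the scales are given to consenting members. No count of non-enrolled contacts by arm is planned, so a reader of the results could not tell whether this had happened.

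**Working it through.** **1. Reproducing the planned size.** Inputs from item 4, Sample Size: "The proportion consenting to testing in the control group will be 0.85"; intervention 0.98; alpha 0.05 (taken as two-sided, which the text does not state); power 90%; "The intra-class correlation (ICC) will be 0.59"; m = 2 contacts per household.

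- Pooled two-proportion formula, mean proportion 0.915: n per arm = [1.96·√(2·0.915·0.085) + 1.282·√(0.85·0.15 + 0.98·0.02)]² / 0.13² = (0.773 + 0.492)² / 0.0169 ≈ 94.6.
- m = 2: design effect 1 + 0.59 = 1.59; 94.6·1.59/2 = 75.2, so 76 households per arm, **152** in total.
- m = 3: design effect 2.18; 94.6·2.18/3 = 68.8, so 69 per arm, **138** in total.

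Both stated figures are reproduced. Power at 152 households is 90.3% (152 contacts per arm, effective n = 152/1.59 = 95.6). The calculation treats every eligible contact as analysed.

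**2. Selection with no true effect.** Assumptions, not in the documents: 85% of all eligible contacts would test in both arms, all control contacts enrol, and a share q of the intervention arm's would-be refusers decline the study.

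Apparent intervention uptake = 0.85 / [0.85 + 0.15(1 − q)].

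| q | Contacts lost (of 152) | Apparent uptake | Spurious gain |
|---|---|---|---|
| 25% | 3.75% (5.7) | 0.85/0.9625 = 88.3% | +3.3 points |
| 50% | 7.5% (11.4) | 0.85/0.925 = 91.9% | +6.9 points |

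These are about a quarter and a half of the planned 13 points.

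**3. Other assumed rates.** If everyone lost would have refused, non-enrolment of 5% gives 0.85/0.95 = 89.5% (+4.5 points) and 10% gives 0.85/0.90 = 94.4% (+9.4). The chance of a falsely significant gain is then about 15% and 55%, against 2.5% nominal in that direction. The whole 13 points would need 1 − 0.85/0.98 = 13.3%, about 20 of 152. If half of those lost would have tested, the figures soften: (0.85 − 0.05·0.5)/0.95 = 86.8% (+1.8) and (0.85 − 0.10·0.5)/0.90 = 88.9% (+3.9).

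**4. The opposite direction.** With a true 0.85 against 0.98 and the same losses in the control arm only, the apparent difference shrinks to 0.98 − 0.883 = 9.7 points or 0.98 − 0.919 = 6.1 points.

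**5. Power of an all-listed analysis.** Assume a share a of listed contacts is absent in both arms and counted as not tested, with 152 listed per arm and ICC 0.59. The proportions become 0.85(1 − a) and 0.98(1 − a). With n = 95.6, power = Φ{[Δ√n − 1.96·√(2p̄(1−p̄))] / √(p₁(1−p₁) + p₂(1−p₂))}.

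- a = 5%: 0.8075 against 0.931; (1.208 − 0.934)/0.469 = 0.58; power about **72%**.
- a = 10%: 0.765 against 0.882; (1.144 − 1.057)/0.533 = 0.16; power about **56%**.

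**The case against.** The strongest reply is that a risk is being treated as a fault. Much of it stands.

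- **A reader might infer that uptake is measured only in enrolled contacts, so that the intention-to-treat label is wrong.** The documents do not say so. Item 13 leaves the denominator open, and the sample size speaks of eligible contacts. What can be said is that it is undefined and that interviews and test offers follow enrolment.
- **A reader might infer that the arm-specific script is shown to change who enrols.** It is not. The wording of the introductory scripts is not given, and the same services are named in both arms. The specified active elements (first tester, prosocial line, opt-out wording, sharing) belong mainly to the later individual offer. The order of introduction and enrolment is itself inconsistent.
- **A reader might infer that consent wording differs by arm.** Section III, item 6 describes a single information sheet and verbal consent document. What differs is the introduction and the team.
- **A reader might infer that the clinic roster should be the primary denominator.** That is a trade-off. It includes people never offered a test and misses contacts found only at home; the plan itself adds two spare kits per visit. It could also misclassify non-enrolled contacts who test through routine services. It moves away from the stated quantity, the proportion consenting to testing, and it costs power.

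These points limit the claim without removing it. Under either order of events, contacts are recruited after allocation by teams that know the arm, and nothing planned would reveal differential enrolment.

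**Conclusion.** The point holds as a recruitment-bias risk combined with an undefined denominator. Followed as written, both uptake and stigma pass through a consent step that comes after allocation and could act differently in the two arms. Direction and size cannot be settled from the documents, which give no non-enrolment rate. The 3.3 to 6.9 points rest on assumed losses of 25% to 50% of would-be refusers in one arm only, with no true effect; they show sensitivity and are not a forecast. They matter because a planned control uptake of 85% leaves few refusers: 6 to 11 missing contacts of 152 are enough. The stated 152 households are reproduced and are not in question.

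**What to change.** 1. Reconcile the two descriptions of the visit in item 4 (Procedures for all households, and subsection a), so that contacts are consented with one identical introduction and consent script in both arms before any arm-specific script is used.
2. Require the household roster (number, age and gender of contacts aged 15 or over) to be completed before the randomisation call. The current text suggests this order but does not fix it.
3. Report, by arm, the numbers of contacts listed, present, eligible, enrolled and offered a test.
4. In item 13, state which contacts form the uptake denominator. Alongside uptake among enrolled or offered contacts, add a sensitivity analysis of all roster-listed contacts aged 15 or over, with the non-enrolled counted as not tested.

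The cost is small: wording changes, a fixed order for a list already collected, and one more analysis. The all-listed analysis will show lower uptake in both arms and, under the assumptions in the working, falls to roughly 72% or 56% power with 5% or 10% absent. It should sit beside the powered comparison and not replace it.
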